8.6. Data management

Data retrieval and management will be conducted separately in each country. Investigator in each country will obtain all necessary permissions and prepare a data application to its country-specific data custodian. A data manager in each country will ensure correctness of the delivered raw data before data management start. Records from different registries will be merged by unique personal identifier or its pseudonym and de-identified before the analysis. Data will be cleaned and coded, and harmonised analytic datasets will be prepared according

to the specifications provided in [Annex 3](#). All four countries use similar coding systems for medications, diagnoses and procedures, and codes will be shared whenever feasible. There may be slight between-country variations in the specific diagnostic or procedure codes, which will be addressed in consultation with clinicians on a country-specific basis. Patient level data are kept on secure servers within each respective country. Patient-level data from Finland, Norway, or Sweden will not be made available to researchers at the ‘vendor organizing institution’ (Aarhus University Hospital, Denmark) or the MAH (Pfizer).

For data management and analyses, SAS version 9.3 or later and/or R version 3.1.1 or later will be used.

8.7. Data analysis

All steps of the country-specific data analyses will be conducted separately in each participating country according to the description below. Each country will generate a set of identical analytic tables, according to the table shells, provided in [Annex 3](#).

After conducting the country-specific data analyses, country-specific datasets containing crude and adjusted estimates of association will be transferred to Aarhus University Hospital, Denmark, for meta-analyses.

8.7.1. Calculation of prevalences of birth outcomes

Prevalence of each birth outcome will be computed as number of newborns with a given outcome divided by the total number of newborns at risk. For the outcomes of congenital malformations and stillbirth in the analysis not including pregnancies ending in 2nd trimester abortion the number of newborns at risk will be the total number of live or stillborn children. For the outcomes of congenital malformations and stillbirth in the analysis including pregnancies ending in a 2nd trimester abortion the number of newborns at risk will be the number of live or stillborn children and the number of pregnancies ending in a 2nd trimester abortion. For the other birth outcome the number of newborns at risk will be the number of liveborn newborns.

8.7.2. Calculation of incidence rates of postnatal outcomes

Incidence rate of each postnatal outcome will be computed as the number of first-recorded events during the follow-up divided by the total person-time at risk contributed by each liveborn infant. The follow-up for each newborn will begin on the date of birth and will end on the date of a given postnatal outcome, emigration, death, or the end of the observation period.

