- during gestation, according to exposure to lamotrigine any time during gestation, according to any in utero exposure to duloxetine, according to any in utero exposure to lamotrigine or duloxetine, and in live or stillborn children unexposed in utero to antiepileptics;
- Estimate the association between any in utero exposure to pregabalin and the birth outcomes other than major congenital malformations, as compared with no exposure to pregabalin; any in utero exposure to lamotrigine; any in utero exposure to duloxetine; any in utero exposure to lamotrigine or duloxetine, and no in utero exposure to antiepileptics.
 - Estimate, in a sensitivity analysis to evaluate potential impact of selection bias, association between first-trimester exposure to pregabalin and prevalence of major congenital malformations, as compared with no first-trimester exposure to pregabalin; first-trimester exposure to lamotrigine; first-trimester exposure to duloxetine; and first-trimester exposure to lamotrigine or duloxetine, in pregnancies ending in livebirth, stillbirth, or 2nd trimester induced abortion (in Denmark, Finland and Norway);

The specific secondary objectives of the study are to:

- Describe, in liveborn infants, the incidence rates (number of incident outcome events/postnatal person time) of pre-specified postnatal neurodevelopmental outcomes (listed in [Section 8.3.2.2](#)) according to exposure (yes/no) to pregabalin any time during pregnancy, after any in utero exposure to lamotrigine, after any in utero exposure to duloxetine, and after any in utero exposure to lamotrigine or duloxetine in pregnancies ending in live birth;
- Estimate, in liveborn infants, the association between in utero exposure to pregabalin and the pre-specified postnatal neurodevelopmental outcomes, as compared with no in utero exposure to pregabalin; any in utero exposure to lamotrigine any in utero exposure to duloxetine, and any in utero exposure to pregabalin or duloxetine.

The calculations of ‘prevalence’ and ‘incidence rate’ are further described in section 8.7.1 and section 8.7.2 respectively.

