All singleton and multiple gestations ending in live birth or stillbirth will be identified in each country's birth registry from 1 January 2005 to 31 December 2015 in Denmark, Finland, and Norway and pregnancies identified from 1 July 2006 to 31 December 2013 in Sweden. As all birth outcomes will have occurred as of the date of delivery, prevalence will be used as a measure of outcome occurrence.¹⁴ However, to allow for delayed reporting/diagnosis, all congenital malformations diagnosis recorded until one year of age will be included, according to the standard procedure used by the European Network of Congenital Anomaly Registers (EUROCAT)¹⁷ through the end of 2016 in Denmark, Finland and Norway and through the end of 2014 in Sweden. In addition, available information on pregnancies ending in 2nd trimester therapeutic induced abortions will be identified in Denmark, Finland and Norway.¹⁸ Information on pregnancies ending in 2nd trimester therapeutic induced abortions is not available from Sweden. It will be especially important to identify pregnancy terminations due to malformations of the nervous system, as nearly half of the pregnancies affected by nervous system malformations may be terminated.¹⁸

For the birth outcomes, stillbirth prevalences at birth will be described and compared among the live and still born infants. For the birth outcomes other than congenital malformations or stillbirth, prevalences at birth will be described and compared.

For the postnatal neurodevelopmental outcomes, live-born offspring of all pregabalin-exposed and the comparator pregnancies will be followed from the date of birth until the earliest record of a given outcome of interest, emigration (except Sweden and Norway, where emigration data are unavailable), death, or end of study (31 December 2014 in Sweden; 31 December 2016 in the other countries); for this analysis children in Norway born before 2008 will be excluded as the Patient Registry of Norway was launched in 2008. Thus, for the neurodevelopmental postnatal outcomes, live-born children will be followed up to a minimum of 1 year and a maximum of 10 years postnatally in Denmark, Finland, and Norway and up to a maximum 8.5 years postnatally in Sweden (Figure 2).

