8.7.5. Secondary analyses

The secondary analyses will be conducted in the following study population/analysis set: pregnancies ending in singleton/multiple live birth. In these analyses any trimester pregabalin exposure will be considered versus each of the comparators as above. The monotherapy subset will be examined, sample size permitting.

Incidence rates (number of events/person-time contributed by live-born infants) of the postnatal neurodevelopmental outcomes will be reported according to any exposure to pregabalin and the predefined comparators. All incidence rates will be reported for any pregabalin therapy and the subset with pregabalin monotherapy.

For the postnatal neurodevelopmental outcomes, exposure will be defined at any time during pregnancy and the same comparators as above. Crude and PS-adjusted hazard ratios will be

estimated using Cox's proportional-hazards regression. In the event that too few postnatal outcomes are observed to estimate association, the number of cases and crude rates will be reported to the extent allowed by the data protection regulation.

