Information bias manifests as misclassification of exposure, outcome or confounders (discussed above). Dispensing records may not accurately represent the actual amount and timing of medication intake (exposure misclassification) and estimation of dose response patterns is limited by the small number of exposed pregnancies. Hospital diagnoses, used in identifying indications, covariates, and outcomes are imperfect measures of true events they purport to measure. Furthermore, as is common in such studies, malformations in pregnancies ending in spontaneous and first-trimester induced abortions cannot be observed, resulting in underestimation of the number of cases. If such selective dropout (i.e. selection bias) is associated with pregabalin exposure, associations based on prevalent outcomes will be biased. Given its design of a fixed study period, the study will be unable to provide equal follow up for live births regarding post neurodevelopmental outcomes. Children of mothers diagnosed and treated for epilepsy during pregnancy may undergo more medical surveillance compared to children of the general population, potentially leading to spurious association observed owing to this detection bias. Due to the limitations of the measurement and case

ascertainment, the study objective and analyses of postnatal outcomes was designated as secondary. Selection bias stemming from inclusion of all eligible pregnancies is of less concern in this study, as study entry for each woman is the estimated conception date of pregnancy and ends for each outcome of interest with the event (e.g. date of live birth, stillbirth). Selection of an appropriate reference group is challenging since no single drug is known to have all the indications of pregabalin and the unexposed population is likely to be healthier than the exposed population. Finally, full feasibility assessment of the postnatal neurodevelopmental outcomes cannot be performed at this time of writing the protocol and prior to review of the data, as those are diagnosed primarily at school age. Not all live-born infants will have follow-up into the school age, and the number of pregabalin exposed pregnancies in the earlier study period may not be sufficient to yield stable estimates of association, as specified in the provided feasibility counts in Table 5 and Annex 3. Emigration data (censoring variable) are not available in the Swedish or the Norwegian datasets, however, the impact of this is likely to be negligible.

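### Neurodevelopmental rates per person-year from birth are not comparable between exposure groups born at different times, and in the sparse-data fallback they are the only between-group result

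*Protocol*

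**What the plan says.** The first secondary objective in section 7 is worded "Describe, in liveborn infants, the incidence rates (number of incident outcome events/postnatal person time", by exposure group. Section 8.7.2 fixes the measure: the count of first-recorded events is "divided by the total person-time at risk contributed by each liveborn infant". It also fixes the clock: "The follow-up for each newborn will begin on the date of birth" and stops at the outcome, emigration, death or the end of observation. Section 8.2 sets that end as a calendar date, "end of study (31 December 2014 in Sweden; 31 December 2016 in the other countries". Sections 8.7.2 and 8.7.5 provide no age bands and no age standardisation for these rates.

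Section 8.9 says that full feasibility of these outcomes could not be assessed, "as those are diagnosed primarily at school age". It adds "Not all live-born infants will have follow-up into the school age" and, because the study period is fixed, "the study will be unable to provide equal follow up for live births". It also warns that exposed pregnancies in the earlier period may be too few for stable estimates.

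Associations are a separate objective, estimated by Cox regression (sections 8.7.3 and 8.7.5). If too few outcomes occur to estimate an association, section 8.7.5 says "the number of cases and crude rates will be reported to the extent allowed by the data protection regulation".

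**The concern.** A crude rate per person-year summarises a group fairly when the hazard is roughly constant over follow-up, or when the groups compared have the same spread of follow-up. Section 8.9 rules out the first. Nothing in the protocol secures the second, because age at cut-off depends on birth date and the birth dates of exposed and unexposed children may differ.

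Pregabalin was approved in July 2004, and its indications were widened in March and September 2006 (section 6). If its use in pregnancy grew through the study window, exposed children are younger at cut-off, spend a larger share of their person-time in preschool years, and show a lower rate with no drug effect. In a safety study that would be falsely reassuring. The consequence is sharpest in the fallback, where no model remains to compare children at the same age.

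**Working it through.** **Figures in the plan.** The protocol gives no expected incidence rate for these outcomes, so there is none to reproduce. Its only precision figure does reproduce. For 3% prevalence, 1000 exposed and a 119:1 ratio, SE = √[(0.97/30)(1 + 1/119)] = 0.1806, and exp[(1.960 + 0.842) × 0.1806] = 1.658, against 1.65845 in section 8.5. It does not bear on this point.

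**Inputs from the protocol (sections 8.2 and 8.3.2).**
- Denmark and Finland: births January 2005 to December 2015, cut-off end of 2016. Possible follow-up F is 1 to 12 years. (Section 8.2 states a maximum of 10 years; its own dates give 12, and 9 for Norway.)
- Norway: births 2008 to 2015, cut-off end of 2016. F is 1 to 9 years.
- Sweden: births July 2006 to December 2013, cut-off end of 2014. F is 1 to 8.5 years.

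**Assumptions (mine; the protocol gives none).**
- Unexposed births are uniform over the window.
- Exposed births change linearly over the window.
- The age-specific hazard is the same in both groups, so the true ratio is 1.0.
- Outcomes are rare; death and emigration are ignored.

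**Formula.** With H(F) the cumulative hazard to age F, the crude rate is E[H(F)] / E[F], averaged over the group's births. The crude ratio divides the exposed value by the unexposed value.

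**Worked case: Denmark/Finland, hazard zero to age 4 and then constant (set to 1), exposed births tripling.**
- Unexposed: E[F] = (1 + 12)/2 = 6.5. E[(F − 4)⁺] = (8²/2)/11 = 2.909. Rate = 2.909/6.5 = 0.4476.
- Exposed: the weight is 1 + 2(12 − F)/11, which integrates to 22. E[F] = 5.583. E[(F − 4)⁺] = (32 + 15.515)/22 = 2.160. Rate = 2.160/5.583 = 0.3868.
- Crude ratio = 0.3868/0.4476 = 0.86, although the true ratio is 1.0.

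**Other cases, crude ratio with no effect.**

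| Assumed hazard | Exposed births | Denmark/Finland | Norway | Sweden |
|---|---|---|---|---|
| Zero to age 4, then constant | double | 0.91 | 0.88 | 0.88 |
| | triple | 0.86 | 0.82 | 0.81 |
| Zero to age 6, then constant | double | 0.87 | 0.82 | 0.81 |
| | triple | 0.79 | 0.72 | 0.70 |
| Zero to age 3, then rising linearly | double | 0.89 | 0.87 | 0.87 |
| | triple | 0.82 | 0.79 | 0.79 |
| One-eighth of later level before age 5 | double | 0.92 | 0.92 | 0.92 |
| | triple | 0.88 | 0.87 | 0.87 |
| One-fifth of later level before age 3 | double | 0.96 | 0.95 | 0.94 |
| | triple | 0.93 | 0.91 | 0.91 |

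With a constant hazard, or with flat use, the ratio is 1.00. If exposed births halve over the window, it is 1.04 to 1.16 across the same five hazards and three windows.

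**Cox check.** In simulated data (Denmark/Finland window, exposed births rising five-fold, no effect, 20 runs of 4000 exposed and 8000 unexposed), the mean crude rate ratio was 0.85. Cox regression on time since birth gave a mean hazard ratio of 1.02.

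**Could the fallback arise?** Table 4 expects 350, 900, 350 and 800 pregnancies exposed at any time, analysed country by country. At Table 5's 1% that is 3.5 to 9 cases per country; at 0.2% it is 0.7 to 1.8. Sparse cells are plausible, most of all for the rarer outcomes.

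**The case against.** The strongest reply is that these rates only describe. Association is estimated by Cox regression with follow-up from birth, year of delivery is in the propensity score (section 8.3.3), and no ratio of crude rates is planned as an effect measure. That is right: a reader who inferred that the hazard ratios are biased by this mechanism would be wrong. It does not cover the fallback, where the model drops out, nor the stated objective of describing rates by exposure group.

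Second, the direction is not established. A reader might infer that the pregabalin rate is certainly too low. The documents do not support that. The approval dates, the remark in section 8.9 about few early exposed pregnancies, and the title of a cited utilisation study point to rising use, but no exposed births by year are given. Nor can exposed births be taken to start from zero: section 8.2 says the start dates were chosen so that pregabalin was already on the market. Duloxetine was also approved in 2004, so its births may shift in the same way.

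Third, a reader might infer that the fallback is the likely result. The counts above make it plausible, not shown. Likewise, crude rates will differ between countries because the windows differ, but comparing rates between countries is not an objective and only estimates of association are pooled.

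Fourth, section 8.9 discloses unequal follow-up and school-age diagnosis, and year of delivery will be tabulated by exposure. A careful reader could notice an imbalance. The disclosure does not draw the consequence for the rates and changes no output. The table shells in Annex 3 are not shown and might contain age bands, but the estimator written in section 8.7.2 and the fallback in section 8.7.5 do not call for them.

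**Conclusion.** The point stands in conditional form. The rate defined in section 8.7.2 depends on each group's birth-year mix as well as on risk, so the crude rates cannot be compared between groups born at different times. If pregabalin-exposed births double or triple over the window while unexposed births are flat, the crude ratio is about 0.70 to 0.96 with no effect. The low end assumes no diagnoses at all before age 6; a modest preschool hazard brings tripling to 0.87 to 0.93. All of these figures rest on assumed birth trends and hazard shapes. What holds without assuming a trend is that the rates are uninterpretable between groups until attained age is taken into account. This is worth correcting because describing the rates is a stated objective and the fallback leaves nothing else.

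**What to change.** In sections 8.7.2 and 8.7.5, add rates by attained-age band (for example 0–3, 4–6, and 7 years and over), or rates for every comparator standardised to the pregabalin group's attained-age distribution. Cumulative incidence by age, with death as a competing event, would serve equally well.

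In the sparse-data fallback, replace the crude rates with observed and expected cases in the pregabalin group, where expected cases are the unexposed age-specific rates multiplied by the exposed person-years in each age band.

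No new data are needed: dates of birth, event and end of follow-up are already required for the planned analysis. The cost is a few sentences and one more table per outcome. Small age cells may have to be merged under data-protection rules; the observed-versus-expected form avoids most of that, because it shows one pair of totals for the exposed group.

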8.7.3. Estimation of prevalence ratios and hazard ratios

Crude and adjusted prevalence ratios and 95% Wald confidence intervals (CIs) for each birth outcome and a given population/contrast will be estimated using log-binomial regression.

Crude and adjusted incidence rate ratios and 95% Wald CIs will be estimated Cox's proportional-hazards regression for each postnatal outcome.

8.7.3.1. Computation of propensity scores

To account for confounding by the measured covariates, adjusted analysis will be conducted using propensity score (PS) stratification, following the approach by Paterno et al.⁴ For each pregnancy, a PS will be computed, using logistic regression, as the probability being exposed to pregabalin vs. given comparator conditional on the measured covariates listed in [Section 8.3.3](#) and [Annex 3](#).⁵³

PS will be estimated for each pregnancy using a generic-outcome model, meaning that all prespecified covariates will be included in the PS-estimating model, regardless of the outcome. Wyss et al showed, in a simulation study, that such model performs well when multiple outcomes are being examined;⁵⁴ furthermore, it is reasonable to assume in this study that all confounders distort the association in the same direction for all outcomes. In case of model non-convergence, covariates with the smallest cell counts (corresponding to the lowest prevalence of covariates) will be removed one-by-one until convergence is achieved.

A separate PS will be estimated for each study population and contrast. To summarise, the following sets of propensity scores will be estimated:

1. First-trimester pregabalin vs. first-trimester unexposed
2. First-trimester pregabalin vs. first-trimester lamotrigine
3. First-trimester pregabalin vs. first-trimester duloxetine
4. First-trimester pregabalin vs. first-trimester duloxetine or lamotrigine
5. First trimester pregabalin monotherapy vs. first-trimester unexposed
6. First trimester pregabalin monotherapy vs. first-trimester lamotrigine monotherapy
7. First trimester pregabalin monotherapy vs. first-trimester duloxetine monotherapy
8. First-trimester pregabalin monotherapy vs. first-trimester duloxetine or lamotrigine monotherapy
9. Any-trimester pregabalin vs. any-trimester unexposed
10. Any-trimester pregabalin vs. any-trimester lamotrigine
11. Any-trimester pregabalin vs. any-trimester duloxetine
12. Any-trimester pregabalin vs. any-trimester duloxetine or lamotrigine
13. Any-trimester pregabalin monotherapy vs. unexposed
14. Any-trimester pregabalin monotherapy vs. any-trimester lamotrigine monotherapy
15. Any-trimester pregabalin monotherapy vs. any-trimester duloxetine monotherapy
16. Any-trimester pregabalin monotherapy vs. any-trimester duloxetine or lamotrigine monotherapy

After estimation of each PS, the following steps will be taken in each country:

- a graph showing distribution of PS of the exposed and unexposed pregnancies will be produced and pregnancies with PS in non-overlapping areas will be deleted (trimming).
- based on the trimmed distributions, strata of PS will be defined using boundaries of the pregabalin-exposed pregnancies. Number of strata will be determined by the number of exposed pregnancies and will vary across countries.
- all exposed and unexposed pregnancies included in a given PS estimation will be classified into these strata based on their PS.
- A weight will be assigned to each unexposed pregnancy based on its stratum; each exposed pregnancy will assigned the weight of 1.
- A weighted regression analysis will be performed, in which adjusted prevalence ratios or adjusted hazards ratios are estimated using a weighted regression model.

Balance of the covariates following trimming and stratifications-strata specific weights will be assessed in each country's dataset using standardised mean differences. Covariates with standardised mean differences <0.1 will be considered balanced. Initially only first-order variables will be entered into the PS models; if imbalance persists, use of interaction terms will be considered. PS will be estimated by an analyst in each country and the final PS models that achieve acceptable covariate balance may be different in each country.

The crude and the adjusted country-specific estimates of association will be reported separately and combined in a meta-analysis (described in [Section 8.7.7](#)).

If feasible, prevalence ratios will be estimated among women with >1 pregnancies discordant with respect to pregabalin exposure in country-specific analyses only (not in meta-analyses).

